# **Secondary Endpoints:**

✓ Difference between the groups in the proportion of events such as death, tracheotomy, invasive ventilation, or continuous non-invasive ventilation ( $\geq 22$  h per day for  $\geq 10$  days);

	✓ Difference between the groups in gripe strength change from baseline at Day 180;
	✓ Difference between the groups in respiratory function (%FVC) change from baseline at day 180;
	✓ Difference between the groups in ALSAQ-40 scores change from baseline at Day 180.
	Safety evaluation including: adverse events (AEs), serious adverse events (SAEs), clinical laboratory tests (hematology, urinalysis, blood biochemistry, thyroid function), vital signs (blood pressure, respiratory rate, pulse and body temperature), 12-lead electrocardiogram (ECG) examination, physical examination.
	Primary safety indicators:
Safety Assessment Indicators	Percentage of subjects with serious adverse reactions within 180 days; (Adverse reactions: AEs related to the IMP)
	Secondary safety indicators:
	Percentage of subjects with adverse reactions within 180 days;
	AEs, SAEs, and their incidence, the clinical manifestations, severity, time of occurrence, end time, duration, treatment measures and outcomes of these are to be recorded, and the correlation between AE and IMP are to be determined.
PK/PD and Biomarkers	The cerebrospinal fluid (Tmax after administration, optional) is to be taken (in part of subjects) at baseline period before administration and 180 days after administration, and the concentration of TBN and its metabolites in cerebrospinal fluid and plasm are to be measured for PK/PD analysis. Biomarkers, such as 3-NT, 8-OHdG, NFL levels in cerebrospinal fluid are to be determined.
Treatment	Subjects need to terminate the treatment permanently if the following events occur:
Termination Termination	✓ The subject is pregnant;
	✓ The subject withdraws informed consent;
	✓ The subject has a medical emergency that requires to terminate the

	treatment permanantly, such as death, tracheotomy, invasive ventilator assisted ventilation, or continuous non-invasive ventilator assisted ventilation (≥ 22 h per day for ≥10 days);  ✓ The subject has a medical emergency requiring a unblinding of the treatment of the subject;  ✓ Determinations based on medical reasons made by investigator.

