# 894 THE MANAGEMENT OF IMP

#### 4.1 Investigational medicinal product (IMP)

#### 901 **4.1.1 Treatment Groups**

900

- 902 (1) TBN tablets: strengths: 100 mg/tablet and 300 mg/tablet, provided by Guangzhou Magpie
- 903 Pharmaceuticals Co., Ltd.
- 904 (2) Placebo: Excipient tablets without TBN, strengths: 100 mg/tablet and 300 mg/tablet,
- 905 provided by Guangzhou Magpie Pharmaceuticals Co., Ltd.

412	Mode	of Ad	minici	tration
4.1.4	vioue	OI AU		Hallon

- Treatment Group 1: TBN tablets 600 mg group (TBN 300 mg × 2 tablets + placebo 300 mg × 2
- tablets are taken orally twice daily, TBN 100 mg  $\times$  6 tablets + placebo 100 mg  $\times$  6 tablets instead
- if the subjects are not able to take 300 mg tablets because of disease progression).
- 910 **Treatment Group 2:** TBN tablets 1200 mg group (TBN 300 mg× 4 tablets are taken orally
- twice daily, TBN 100 mg  $\times$  12 tablets instead if the subjects are not able to take 300 mg tablets
- 912 because of disease progression).
- 913 **Control Group:** placebo group (placebo 300 mg × 4 tablets are taken orally twice daily, placebo
- $100 \text{ mg} \times 12 \text{ tablets instead if the subjects are not able to take } 300 \text{ mg tablets because of disease}$
- 915 progression).

- **Dosage and Administration:** orally administered, twice a day, once in the morning and evening
- 917 (or the interval  $\geq 8$  hours), at least 1 hour before meals ( $\geq 1$  hour before meals) or at least 2 hours
- after meals ( $\geq 2$  hours after meals), for  $180 \pm 3$  days.
- Note: If the subjects are not able to take 300 mg tablets of TBN or placebo because of disease
- progression, the tables may be exchanged for the 100 mg/tablet, with no change in the dose.
- During the treatment, subjects should record the time and dose of the drug in the subject's diary
- 922 card. Any adverse reactions should be promptly treated and recorded in the original medical
- 923 records.

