# 924 **4.2** Preparation/Package/Storage/Responsibility

# 925 4.2.1 Packaging and Labeling of IMP

- 926 Packaging specification: the packaging material is 60 ml oral solid medical high-density
- 927 polyethylene (HDPE) bottle with child protection cover, containing silica gel desiccant and
- 928 deoxidizer, 25 pills/bottle.
- The labels of 100 mg TBN tablets/placebo and 300 mg TBN tablets/placebo are as follows:

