- That is, multiple signs, symptoms, and laboratory abnormalities can be called or attributed to a
- disease or impairment, then this is treated as an adverse event. Symptoms/signs will be used if
- the diagnosis cannot be made definitively. When the diagnosis is clear at a later stage, the record
- should be updated to replace the previous symptoms/signs with the diagnosis.
- 1057 When determining the names of AEs, ensure that each adverse event name consists of a single
- event. One diagnosis, sign/symptom is one adverse event. Therefore, when a subject presents
- with symptoms of "vomiting and diarrhea," the adverse event name should be recorded as two
- 1060 AEs, e.g., (1) diarrhea and (2) vomiting, rather than one "diarrhea and vomiting" for both
- symptoms. If the laboratory test abnormality is part of a syndrome, record the syndrome or
- diagnosis (e.g., anemia) rather than the laboratory test result (i.e., decreased hemoglobin).
- AEs are recorded according to the latest edition of the International Medical Dictionary for
- 1064 Regulatory Activities (MedDRA) as "System Organ Class (SOC)" and "Preferred Term
- 1065 (PT)". "Preferred Term (PT). Describe the number of cases, number of occurrences and incidence
- of all AEs, all TEAEs, TEAEs related to IMP, serious TEAEs, serious TEAEs related to IMP,
- TEAEs leading to withdrawal from the trial, TEAE-related deaths, etc., according to treatment
- 1068 group.

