#### 1372 **8.2** Analysis Population

- 1373 This study used three data sets: Full Analysis Set, Per-Protocol analysis set, and Safety analysis
- 1374 set.
- 1375 Full Analysis Set (FAS): A collection of all randomized subjects with at least one study
- administration and at least one valid post-dose efficacy evaluation data. FAS is the primary
- analysis set. The FAS will be used to analyze the subject's distribution, demographic data, and
- 1378 baseline characteristics and efficacy. Subjects will be analyzed according to their randomized
- 1379 groups.
- Per-Protocol Set (PPS): It included FAS subjects who meet the main inclusion criteria and do not
- meet the main exclusion criteria, complete the treatment without any major protocol deviations.
- The PPS is mainly used for the sensitivity analysis of efficacy.
- Safety analysis set (SS): A collection of subjects with at least one administration and actual
- safety data of the post study administration. Missing safety values are generally not carried
- forward. SS will be used for safety analysis. Subjects will be analyzed according to randomized
- 1386 groups.

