# 1412 8.3.4 Analysis of Secondary Efficacy Endpoint

- 1413 The following four secondary efficacy endpoints, the continuous data of each visit in different
- groups will be described using mean  $\pm$  standard deviation and median (minimum, maximum).
- 1415 Comparing with the baseline data, the paired T test is to be used to compare the within-group
- before-after differences. Analysis of variance (ANOVA) is to be used before and after treatment
- between groups. For the first secondary endpoint (endpoint event and disease exacerbation
- event), Kaplan-Meier plots will be used to describe the survival rate of patients without endpoint
- event, and Log-Rank test or non-parametric statistical method is to be used to compare the
- indicators of each group.
- 1421 (1) Proportion of endpoint events, including death, tracheotomy, invasive ventilator-assisted
- ventilation, or continuous non-invasive ventilator-assisted ventilation ( $\geq$  22 h per day for  $\geq$
- 1423 10 days);
- 1424 (2) Difference between the groups in grip strength change from baseline at Day 180;
- 1425 (3) Difference between the groups in respiratory function (%FVC) change from baseline at
- 1426 Day 180;
- 1427 (4) Difference between the groups in ALSAQ-40 scores change from baseline at Day 180.
- 1428 **8.3.5 Safety Assessment**
- Descriptive statistical analysis is mainly to be used to list the AE and SAE, drug-related AE and
- SAE that occurs in this trial, and between-group comparisons are conducted using the  $X^2$  test or
- 1431 Fisher's test.
- 1432 Descriptive statistics are to be used to summarize laboratory tests, vital signs, and
- electrocardiograms, etc. Shift tables are to be used to describe changes in normal/abnormal
- results before and after administration, such as laboratory tests, electrocardiograms, and physical
- 1435 examinations.
- 1436 **8.3.6 Interim Analysis**
- 1437 Not Applicable

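### Section 8.2 groups the safety set by randomised arm instead of treatment received, so a reaction in a subject who took another arm's product is counted in the wrong arm

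*Protocol*

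**What the plan says.** Section 8.2 of the protocol defines membership of the safety set by dosing and follow-up data: "Safety analysis set (SS): A collection of subjects with at least one administration and actual" safety data after dosing. The word "actual" there qualifies the safety data, not the treatment. The section then fixes the grouping: "SS will be used for safety analysis. Subjects will be analyzed according to randomized" groups. The paragraph on the full analysis set (FAS) gives the same rule: "baseline characteristics and efficacy. Subjects will be analyzed according to their randomized" groups.

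Three other places use the safety grouping, and none changes it:

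- The synopsis names the primary safety indicator: "Percentage of subjects with serious adverse reactions within 180 days; (Adverse reactions: AEs related to the IMP").
- Section 8.3.5 describes the adverse events and the "SAE that occurs in this trial, and between-group comparisons are conducted using the" chi-square or Fisher test. It does not say how the groups are formed.
- Section 6.1.3 asks for event counts, including "TEAEs leading to withdrawal from the trial, TEAE-related deaths, etc., according to treatment" group. It does not say whether this means assigned or received treatment.

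**The concern.** Grouping by randomised arm protects an efficacy comparison, because it preserves the balance that randomisation created. A safety table asks a different question: what happened to the people who took each product. Under section 8.2, a subject randomised to placebo who took TBN and had a reaction appears as a placebo reaction. A subject randomised to TBN who took placebo stays in the TBN denominator without having been exposed.

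Where the product raises the reaction rate, both errors shrink the apparent difference, which is the unfavourable direction for a safety analysis. The same applies between 600 mg and 1200 mg, and exploring the dose is one of the study objectives (section 2).

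This is more than a detail left to the statistical analysis plan. The protocol states the rule outright, so a plan that grouped by treatment received would contradict section 8.2.

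**Working it through.** The protocol gives no rate or power figure tied to this rule, so there is no stated number to reproduce. The check has two parts.

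**1. Text.** The passages on safety grouping are the synopsis safety indicators and sections 3.3.2, 6.1.3, 8.2 and 8.3.5. Only section 8.2 says how subjects are grouped, and it says by randomised arm. No passage says by treatment received.

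**2. Size of the effect.**

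Inputs:
- n = 50 per arm (section 8.1).
- k = number of swapped pairs: k subjects in one arm took the other arm's product throughout, and k the reverse. The protocol gives no figure; 1, 2 and 5 are assumed.
- p_T and p_P = true reaction rates on TBN and placebo. The protocol gives none for ALS patients; three assumed pairs are shown.

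Formulas when subjects are analysed as randomised:
- Observed TBN rate = ((n − k)·p_T + k·p_P)/n
- Observed placebo rate = ((n − k)·p_P + k·p_T)/n
- Observed difference = (p_T − p_P)·(1 − 2k/n)

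Worked example, 10% vs 0%, k = 1: TBN (49 × 10%)/50 = 9.8%; placebo (1 × 10%)/50 = 0.2%; difference 9.6 points.

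| Assumed true rates | True difference | k = 1 | k = 2 | k = 5 |
|---|---|---|---|---|
| 10% vs 0% | 10.0 | 9.6 | 9.2 | 8.0 |
| 20% vs 5% | 15.0 | 14.4 | 13.8 | 12.0 |
| 5% vs 0% | 5.0 | 4.8 | 4.6 | 4.0 |

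(Differences in percentage points.)

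A one-way error, in which one placebo subject takes TBN and no TBN subject takes placebo, costs half as much: 10 × (1 − 1/50) = 9.8 points.

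Grouping by treatment received restores the true difference in every row. With k = 0 the two rules agree.

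**Average against worst case.** One subject is 1/50 = 2 points of an arm. Suppose 2 of 50 subjects taking TBN react and none of 50 on placebo, with one swapped pair. If the swapped TBN-taker is one of the two reactors, the table reads 1/50 vs 1/50 and a 4-point difference vanishes. The chance of that is 2/50 = 4%, so the average loss is 4% × 4 = 0.16 points. The formula agrees: 4 × 2/50 = 0.16.

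**The case against.** The strongest reply is that the rule does nothing unless someone takes another arm's product, and that the protocol guards against this. The IWRS issues the random number and drug code (section 5.1), each bottle's use and return is recorded (section 4.2.2), and the monitor checks quantities against dispensing records (section 4.2.3). This stands and limits the severity. It does not justify the rule, which gives the wrong answer in exactly the cases where it matters.

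A reader might also infer more than the documents support:

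- *That wrong product is likely here.* The 600 mg arm mixes active and placebo tablets ("TBN tablets 600 mg group (TBN 300 mg × 2 tablets + placebo 300 mg × 2" tablets, twice daily), bottles are small ("deoxidizer, 25 pills/bottle"), and 8 tablets a day for 180 days is 8 × 180/25 = 57.6 bottles per subject. But bottles are not independent chances of error. The trial schedule dispenses product at six time points, so about 6 × 150 = 900 dispensing events in all. One wrong bottle covers 25/8, or about three days. A relative collecting the product does not change the code dispensed.
- *That one misattribution removes a safety signal.* That is the worst case above, with a 4% chance under its own assumptions. In any case 2/50 vs 0/50 gives a two-sided Fisher p of 0.495, so no statistical signal existed to lose.
- *That this is the drug's first study in patients.* Section 1.2.4 says only that no efficacy study of the tablets in patients has been done; it reports an ongoing phase II trial of the injection.
- *That requiring post-dose safety data is part of the same fault.* It is a separate matter. Adding subjects with no recorded events would only enlarge the denominator and lower the reaction rates.

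**Conclusion.** Wrong as written, and should be fixed; the likely magnitude is low. Section 8.2 applies the efficacy grouping to safety, and nothing else in the protocol overrides it. The effect is zero without wrong-product exposure. With one to five swapped pairs among 50 per arm, it removes 4% to 20% of the true difference (2k/n = 2/50 to 10/50).

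These figures assume that the swapped subjects took the wrong product throughout and that reaction risk depends on the product taken. Shorter exposure would usually mean less dilution. The direction, towards no difference, holds on average for the two arms that exchanged product. It need not hold for each of those arms against the third: a 600 mg subject who took 1200 mg could raise the apparent difference between 600 mg and placebo.

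**What to change.** Change the sentence in section 8.2 so that safety-set subjects are analysed according to the treatment actually received. Leave the FAS grouped as randomised.

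State before unblinding how a subject with mixed exposure is classified. One workable rule is to use the treatment taken for most of the dosing period and flag any exposure to another arm's product. A rule that moves a subject to the highest dose ever taken is harder to defend: one wrong bottle late in the study would reassign months of follow-up on the randomised product. Require a listing of all subjects whose actual and randomised treatment differ.

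The cost is a changed sentence and a short classification rule in the protocol, matched in the statistical analysis plan. No new data are needed: the IWRS, the accountability records and the diary cards already record what was dispensed, returned and taken.

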# 8.3 Statistical Method

1387

1388

#### 8.3.1 Enrollment Analysis

- List the number of enrolled and completed subjects in total and for each site. Identify three
- analysis data sets (FAS, PPS, SS). List the reasons for excluding subjects from the PPS."
- The disposition of missing values data is detailed in the statistical analysis plan.

#### 1392 **8.3.2 Demographic Data and Baseline Analysis**

- 1393 Descriptive statistical demographic data and other baseline characteristics:
- Continuous variables: Calculate the number of subjects, mean, standard deviation (SD),
- median (Q1, Q2), minimum, and maximum;
- Count data and categorical data to calculate frequency and composition ratio;
- Perform a difference test between groups, with P values listed as exploratory results.

# 1398 **8.3.3 Primary Efficacy Endpoint Evaluation**

- 1399 The primary endpoint is difference between the groups in the ALSFRS-R score change from
- baseline at Day 180.
- 1401 ALSFRS-R data of each visit in different treatment groups are statistically described by mean ±
- standard deviation and median (minimum and maximum). Comparing with the baseline, the
- paired T test is to be used to compare the within-group before-after differences. Analysis of
- variance (ANOVA) is used for comparing changes before and after treatment in each group, and
- the linear model will include three random stratification factors. The Tukey method-corrected 95%
- 1406 confidence interval for each group's least squares means (LS Means) and Least Squares Means
- Difference is to be calculated according to the model's least squares means (LS Means) to
- compare the statistical differences between the two groups. The model is to be used to further
- investigate the interaction between groups and three random stratification factors. If there is a
- 1410 qualitative interaction, a subgroup analysis of the relevant random stratification factors will be
- 1411 performed.

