#### 1.3.2. Known potential benefits

- The benefits of TBN for ALS treatment include three aspects:
- 512 1) Nonclinical studies have shown that TBN was effective in the treatment of ALS. 10, 30, and
- 513 60 mg/kg of TBN can improve motor behavioral deficits caused by loss of spinal cord motor
- neurons in a mice model of ALS, markedly reduce the expression of SOD1 in the spinal cord,
- and significantly reduce the atrophy of muscle fibers of the gastrocnemius muscle, as well as
- improve the survival of motor neurons in the spinal cord and attenuating astrocyte activation.
- 517 2) TBN has good blood-brain barrier permeability, which is crucial for diseases in central
- 518 nervous system. TBN has strong free radical scavenging ability, which can attenuate
- 519 mitochondrial damage caused by oxidative stress. TBN can inhibit calcium inward flow. TBN
- also has anti-inflammatory activity. TBN can activate the AMPK/PGC1 pathway/Nrf2/HO-1
- 521 pathway, which improves the mitochondrial function, and thus attenuates damage in neuronal
- 522 cell. These properties suggest that TBN is a potential ALS treatment.
- 523 3) The combination of TBN and riluzole is expected to be safe. The two drugs have different
- mechanisms of action (riluzole acts by inhibiting excitatory neuronal activation and TBN acts
- mainly by scavenging free radicals), and it is expected there may be a synergistic effect in
- efficacy. In vitro findings suggesting that the combination of riluzole with CYP1A2 inhibitors or
- 527 inducers may increase or decrease the blood concentration of riluzole, thereby increasing the
- 528 adverse effects of riluzole or affecting its efficacy. The results of nonclinical studies have
- demonstrated that TBN has no inhibitory or inducing activity on CYP1A2. Therefore, drug-drug
- interactions between TBN and riluzole are unlikely to occur.

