#### **3.5.3.2 Items of Clinic Visit**

- Each clinic visit should evaluate and record the occurrence of AEs, concomitant medication,
- dispense IMP and return the unused IMP, and dispense and return of diary cards.
- 723 V2, V4: weight, ALSFRS-R score, grip strength, respiratory function (%FVC), vital signs,
- 724 physical examination, electrocardiogram, hematology, urinalysis, blood biochemistry, urine
- 725 pregnancy, and thyroid function will be test.
- 726 V7: Weight, physical examination, vital signs, hematology, urinalysis, blood biochemistry,
- 727 thyroid function, 12-lead electrocardiogram, respiratory function (%FVC), grip strength,
- 728 ALSFRS-R scale, ALSAQ-40 scale, centralized blood collection (if consent), cerebrospinal fluid
- 729 collection (if consent), and urine pregnancy in women of childbearing age.

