# 5 METHODS FOR REDUCING BIAS: RANDOMIZATION AND BLINDING

#### 5.1 Randomization

975

976

- 977 This study uses Interactive Web Response System (IWRS) to dispense random numbers and
- 978 corresponding IMP. Subjects' random numbers are generated by independent statisticians
- 979 unrelated to the study using SAS 9.4 software or higher version. The subject-drug randomization
- table is in duplicate, sealed and handed over to the main study unit and the sponsor.
- After a 90 day observation period, eligible subjects are to be randomly assigned to high or low
- dose of the IMP group or placebo group (1:1:1). The investigator log into the IWRS system,
- 983 where they are to be given a random number and a drug code.
- In order to ensure that the number of patients in each trial group is similar and the distribution of
- 985 important prognostic factors is balanced, this study uses the minimization method in dynamic
- 986 randomization. The stratification factors are: the diagnostic grade of ALS (clinical diagnosis vs
- 987 clinical diagnosis and laboratory support The diagnostic criteria for clinical diagnosis), the
- 988 change in ALSFRS-R scores during observation period (-1 or -2 vs -3 or -4) and age (<65 years
- 989 vs >65 years).
- 990 Once having been randomly assigned in the study, subjects withdrawing from the clinical trials
- 991 for any reason, regardless of whether or not having been administered with the IMP, will retain
- their random number and the subject will not be allowed to subjects in the trial again.

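### The primary model for ALSFRS-R change lists the three minimisation factors but not baseline ALSFRS-R, and the secondary ANOVAs state no terms at all, so the analyses are less precise than the data allow.

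*Protocol*

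**What the plan says.** Protocol section 8.3.3 begins "The primary endpoint is difference between the groups in the ALSFRS-R score change from" baseline at Day 180. The sentence on method reads in part "variance (ANOVA) is used for comparing changes before and after treatment in each group, and" and continues "the linear model will include three random stratification factors". Tukey-corrected 95% intervals for the least squares mean differences come from that model. No other term is named for the main comparison.

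Section 5.1 describes the minimisation: "randomization. The stratification factors are: the diagnostic grade of ALS", followed by "change in ALSFRS-R scores during observation period (-1 or -2 vs -3 or -4) and age" (cut at 65 years). The second factor is the decline during screening, not the score at randomisation. The trial schedule and section 3.5.2 place an ALSFRS-R assessment at baseline for every subject.

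For grip strength, %FVC and ALSAQ-40, section 8.3.4 says only "Analysis of variance (ANOVA) is to be used before and after treatment" between groups. It mentions neither a baseline covariate nor the minimisation factors. The event endpoint in the same section is handled by Kaplan-Meier and a log-rank or non-parametric test, so this point does not concern it.

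Section 8 leaves detailed description to the SAP, and section 8.3.1 leaves missing values to it. Section 8.1 plans 50 subjects per group with no statistical assumptions and no sample-size calculation.

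**The concern.** When an outcome is change from baseline, the baseline value is normally the first covariate considered, because change often correlates with the starting level. Here the protocol goes as far as listing the adjustment factors for the primary model, and baseline is not on the list. Section 8.3.2 plans between-group tests of baseline characteristics, so the plan looks for baseline imbalance but gives the primary model no term that would respond to it.

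Precision is what is at stake. The group size was not derived from any target, and section 3.1.4 says that the trial is meant to support phase 3. A narrower interval for each dose-placebo difference is therefore directly useful, and it can be had from data already being collected.

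The secondary models raise a related question. Allocation balances the three factors. If an analysis then ignores them, the variation they explain stays in the residual although it no longer contributes to the difference between groups. The standard error is then too large.

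**Working it through.** The protocol states no SD, correlation or power, so there is no figure of its own to reproduce.

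**Inputs from the protocol.** 50 subjects per group; three groups; two-sided 0.05; Tukey correction. Section 3.1.1 cites a 2.5-point difference for edaravone at 6 months. It is used here only as a yardstick, since it is not a design assumption.

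**Assumptions.** SD of change 4 to 7 points. Within-group correlation r of baseline with change, given the three factors, 0 to 0.5. Share R² of a secondary outcome's variance explained by the factors, 0.05 to 0.20.

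**Precision of the primary contrast.** Var(ANCOVA) = Var(ANOVA) × (1 − r²). The equivalent group size is 50 / (1 − r²). At SD 5 the unadjusted standard error is 5 × √(2/50) = 1.00. The Tukey critical value for three groups on 144 degrees of freedom (150 − 1 − 2 − 3) is 2.37.

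| r | Variance cut | Equivalent n per group | Tukey half-width, SD 5 | Pairwise power for 2.5 points, SD 5: alpha 0.05 / Tukey |
|---|---|---|---|---|
| 0 | 0% | 50.0 | 2.37 | 70.5% / 55.2% |
| 0.1 | 1% | 50.5 | 2.36 | 71.0% / 55.7% |
| 0.2 | 4% | 52.1 | 2.32 | 72.3% / 57.3% |
| 0.3 | 9% | 54.9 | 2.26 | 74.6% / 60.0% |
| 0.4 | 16% | 59.5 | 2.17 | 77.9% / 64.0% |
| 0.5 | 25% | 66.7 | 2.05 | 82.3% / 69.8% |

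Moving from r = 0 to r = 0.3 at other SDs, power at alpha 0.05 goes from 87.8% to 90.6% (SD 4), 54.9% to 58.9% (SD 6) and 43.1% to 46.5% (SD 7). The covariate uses one degree of freedom, which costs roughly 1/143 = 0.7% of variance, so at r = 0.1 gain and cost nearly cancel.

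**Chance imbalance.** The baseline difference between two groups of 50 has standard error √(2/50) = 0.20 baseline SD, so its 95% range is ±1.96 × 0.20 = ±0.39 SD. The unadjusted contrast moves by slope × imbalance, which equals r × SD of change × 0.39:
- r = 0.2: 0.39 to 0.47 points (SD 5 to 6)
- r = 0.3: 0.59 to 0.71 points
- r = 0.5: 0.98 to 1.18 points

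This is the same loss seen from another side. At r = 0.3 and SD 5 the shift has standard deviation 0.3 × 1.00 = 0.30, and 0.30² = 0.09 is the 9% of variance in the table.

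**Secondary endpoints.** If perfectly balanced factors are left out, a nominal 5% test has true size 2 × (1 − Φ(1.96 / √(1 − R²))). This gives 4.4% at R² = 0.05, 3.9% at 0.10 and 2.8% at 0.20. The error runs in the conservative direction.

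**The case against.** The other side has a good case on several counts. Under randomisation the change-score ANOVA is unbiased on average. The shift from a chance imbalance already lies inside the confidence interval. The gain may be small: entry requires every ALSFRS-R item to be at least 2 and respiratory function to score 4, which narrows the baseline range, and the model already adjusts for screening decline. At r = 0.3 the standard error falls only from 1.00 to √0.91 = 0.954. The trial is exploratory. All of this stands, and it limits the point to efficiency.

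It can also be said that the wording on included factors is not an exhaustive list and that the SAP may add terms. That carries weight for section 8.3.4, which is silent. It carries less for section 8.3.3, where the terms are named and an added covariate would alter the stated primary model.

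Four stronger readings might be inferred, and the protocol supports none of them:
- *A baseline difference passes whole into the treatment contrast.* The outcome is already a change score, so only slope times imbalance remains.
- *Section 8.3.4 rules out adjustment.* It states no terms, which is not exclusion.
- *Dropout biases the comparison, so a repeated-measures model is required.* Section 3.5.3.2 does collect interim values ("V2, V4: weight, ALSFRS-R score, grip strength, respiratory function (%FVC), vital signs"), but a completers-only analysis is nowhere specified. The full analysis set needs only one valid post-dose efficacy evaluation, and missing values are left to the SAP.
- *Riluzole must be a covariate.* Section 1.3.2 says "it is expected there may be a synergistic effect in" efficacy. Synergy would be a treatment-by-riluzole interaction, which a main-effect term does not test, and riluzole is not an allocation factor.

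**Conclusion.** The point holds as a moderate loss of efficiency, not an error of validity. It is firm for the primary endpoint: section 8.3.3 lists the adjustment terms and baseline ALSFRS-R is not among them. For grip strength, %FVC and ALSAQ-40 it is a request to state terms that section 8.3.4 leaves open.

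The size rests on a correlation that the protocol does not give. The variance saved is negligible at r = 0.1, 9% at 0.3 and 25% at 0.5. Conservatism in the secondary tests arises only if the minimisation factors are in fact left out, and its extent depends on how much variance they explain. The change is worth making because it costs almost nothing, even if the gain proves to be at the low end.

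**What to change.** In section 8.3.3, specify an ANCOVA of Day 180 ALSFRS-R change on treatment, baseline ALSFRS-R and the three minimisation factors, keeping the Tukey-corrected contrasts. In section 8.3.4, specify an ANCOVA for grip strength, %FVC and ALSAQ-40, each with treatment, its own baseline and the same three factors.

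The cost is wording, plus one degree of freedom in the primary model (144 to 143 residual) and four in each secondary model. No new data or visits are needed. The change should be fixed before unblinding.

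A repeated-measures version that uses Days 30 and 90 for ALSFRS-R, grip strength and %FVC is an option. It is best settled together with the SAP's missing-data plan, since most of its advantage over ANCOVA depends on that plan. ALSAQ-40 is scheduled only at baseline and Day 180 (or withdrawal), so ANCOVA suits it in any case.
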